## 9.4 Statistical Methodology

### 9.4.1 Data Summary

The following is a detailed proposal of statistical analyses planned for data collected during the study.

Descriptive statistics will be computed for all preoperative conditions and demographic parameters. That is, for continuous data (e.g. KSS) the N, mean, median, standard deviation, minimum and maximum will be computed. For categorical data (e.g. gender) the frequency will be computed. If appropriate, the data will be presented by appropriate subgroups (e.g. center).

Descriptive statistics and statistical comparisons for important demographic, efficacy and safety variables will be provided in tables.

Statistical analyses will use SAS® software version 9.1 or higher.

### 9.4.2 Sample Size Calculation

A total of 181 cases implanted with the Triathlon TS Total Knee System will be enrolled in the study. The mean total KSS improvement expected, as compared from preoperative to 2 years postoperative, is 70 points. It is assumed that the mean total KSS improvement from preoperative to 2 years postoperative for cases implanted with the Triathlon TS Total Knee System will be comparable to the expected rates (not 10% or 7 points worse), above 63 points. Given a standard deviation of 35 for the improvement in scores, 80% power, and a one-sided 0.05 alpha level to test the 10% (7 points) non-inferiority hypothesis, a sample size of 154 subjects will be required to meet the primary efficacy objective. By factoring in a 15% lost to follow-up rate within 2 years, a total enrollment of 181 subjects will be needed.

### CONFIDENTIAL

### 9.4.3 Interim Analyses and Early Stopping Considerations

No interim analysis is planned.

### 9.4.4 Efficacy Patient Populations

### 9.4.4.1 Efficacy

**Per Protocol Population**: The study population for analysis will include all subjects who receive the Triathlon TS Total Knee System. This does not include cases censored from analysis for a reason that may have a significant impact on outcome.

The primary and secondary efficacy analyses will be based on the per protocol population.

### 9.4.4.2 Safety

Safety Population: The study population for analysis will include all subjects who receive the Triathlon TS Total Knee System. This does not include cases censored from analysis for a reason that may have a significant impact on outcome.

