## 3.3 Number of Subjects

Cases will be enrolled in this study until 181 receive the Triathlon TS Total Knee System as required under this protocol. All cases will receive, at a minimum:

- Triathlon TS Femoral Component in a cemented application
- Triathlon TS Plus Tibial Insert or the Triathlon Posteriorly Stabilized (PS) Tibial Insert
- Triathlon TS Universal Tibial Baseplate in a cemented application.

The subject's patellar component may or may not be revised, based upon surgeon discretion. If revised, a Triathlon Patellar Component must be used, and in a cemented application. Additionally, a variety of device accessories may be used. All components are described in detail in Section 6 of this protocol, Device Description.

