### 9.4.4.4 Censored Cases

In the event that a protocol deviation occurs which could affect subject outcome, the data for the affected subject will be censored from the Efficacy and Safety Subject Populations. All cases that fall into this category will be reported separately.

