## 10.3 Early Withdrawal of Subjects

### When and How to Withdraw Subjects

In the event that a subject is discontinued by the investigative center prior to the final study evaluation, the subject will be notified by the center that they are no longer in the study and a Study Termination CRF will be completed.

The following is a list of reasons for which subjects may be withdrawn and the date of termination that should be used on the Study Termination CRF in each situation. This list is not all inclusive:

Termination Reason	Date of Termination
Death	Date of death
Investigative center termination	Date of study close-out visit
Lost to follow-up	Date Stryker termination approval given
Voluntary withdrawal	Date subject notified center of withdrawal
Revision/removal of study device	Date of revision/removal procedure
Study device not implanted	Date of surgery
Surgery not performed	Date Stryker termination approval given

At the time of study surgery it is required that the following components are implanted:

- Triathlon TS Femoral Component
- Triathlon TS Universal Tibial Baseplate
- Triathlon TS Plus Tibial Insert or Triathlon PS Tibial Insert

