### CONFIDENTIAL

## 11.6 Protocol Deviations

Any deviation from this protocol will be reported to or identified by Stryker and will be reported to the EC/IRB according to their required reporting procedures. Protocol Deviations for this study include, but are not limited to, the following:

- Informed consent deviations, including but not limited to:
  - $\circ$  Study procedures performed prior to informed consent
  - o Incorrect informed consent version used
- Patient enrolled does not meet the inclusion/exclusion criteria
- Protocol specified study component(s) not implanted
- Unavailable primary endpoint

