### CONFIDENTIAL

Serious complications may be associated with any total joint replacement surgery. These complications include, but are not limited to: infection; genitourinary disorders; gastrointestinal disorders; vascular disorders, including thrombus; bronchopulmonary disorders, including emboli; myocardial infarction and death.

With all implanted devices, asymptomatic, localized progressive bone resorption (osteolysis) may occur around the prosthetic components as a consequence of foreign-body reaction to the particulate matter of metal or UHMWPE. Particulate is generated by interaction between components as well as adhesion, abrasion and fatigue. Secondarily, particulates can also be generated by third body wear. Osteolysis can lead to future complications, including loosening, necessitating the removal and replacement of prosthetic components.

Early and late loosening of total knee components can occur. Early biomechanical loosening may result from inadequate initial fixation, latent infection, premature loading of the prosthesis or trauma. Late loosening may result from trauma, infection, biological complications including osteolysis or mechanical problems, with the subsequent possibility of bone erosion/pain.

Peripheral neuropathies, circulatory compromise and heterotopic bone formation may occur.

Intraoperative fissure, fracture, or perforation of the femur or tibia can occur due to impaction of the component into the prepared femur or tibia. Postoperative femoral or tibial fracture can occur due to trauma, the presence of defects or poor bone stock.

Metal sensitivity reactions have been reported following joint replacement.

AEs may necessitate reoperation, revision, arthrodesis of the involved joint or amputation of the limb.

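### Safety Population limited to device recipients: an attempted implantation that is abandoned cannot enter the adverse event rates

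*Combined protocol and SAP*

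**What the plan says.** - **Population.** Section 9.4.4.2 states: "The study population for analysis will include all subjects who receive the Triathlon TS Total Knee System". It then adds: "This does not include cases censored from analysis for a reason that may have a significant impact on outcome". Section 9.4.4.3 limits the survival analysis to recipients in the same way, and so does the efficacy population in 9.4.4.1.
- **Count.** Section 3.3 reads: "Cases will be enrolled in this study until 181 receive the Triathlon TS Total Knee System as required under this protocol". A case that does not receive the system does not count towards 181, and enrolment continues past it.
- **Non-implantation.** The table of withdrawal reasons in 10.3 includes "Study device not implanted", with termination dated to the day of surgery. Section 11.6 lists "Protocol specified study component(s) not implanted" as a protocol deviation.
- **Deviations.** Under 9.4.4.4, when a deviation could affect outcome, "the data for the affected subject will be censored from the Efficacy and Safety Subject Populations". The section continues: "All cases that fall into this category will be reported separately".
- **Collection and analysis.** Section 8.1 makes reportable events collectable from consent. Section 9.2.2 lists and tabulates all adverse events and presents rates with 95% confidence intervals. Sections 2.2 and 12.3 set those rates against published ones.
- **The risk itself.** Section 12.2 recognises that "Intraoperative fissure, fracture, or perforation of the femur or tibia can occur due to impaction of the component". Section 12.3 repeats intraoperative fracture among the expected complications.

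**The concern.** Membership of the Safety Population is settled at the end of surgery, but some of the events it is meant to count happen during surgery. If such an event makes the surgeon give up on the study system, the event removes its own subject from the rate. Selection into the denominator can then depend on the outcome being measured.

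The study has one arm, so no concurrent group shares the distortion. The affected rates are the ones the safety objective compares with the literature. What is at stake is a small set of figures, the rates of intraoperative and early complications and their intervals. Efficacy is not touched.

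**Working it through.** **1. Follow one abandoned case through the plan.** Take a subject who consents, goes to surgery, has a fracture during impaction, and leaves without the study system.

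- Event collected? Yes (8.1, from consent).
- Counted towards 181? No (3.3).
- In the efficacy, safety or survival population? No. All three require receipt (9.4.4.1 to 9.4.4.3).
- Event visible in the report? Probably. Section 9.2.2 lists all adverse events, and 9.4.4.4 reports a case separately if it is treated as a censored deviation. The plan does not say whether a case without the implant counts as censored.
- In the rate and its interval? No. Section 9.2.2 names no denominator of its own, and the only safety denominator defined is that of recipients.

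**2. Arithmetic of the rate.** The plan gives no figure for abandoned cases. Its only usable number is 181, which follows from 9.4.2 as 154/(1 − 0.15) = 181.2. Let x be the implanted cases with a given intraoperative event, a the abandoned attempts, and b those among the a that had the event.

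Planned rate = x/181. Rate over attempts = (x + b)/(181 + a).

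The second exceeds the first when 181(x + b) > x(181 + a), that is, when b/a > x/181. Where abandonment was caused by the event, b = a and the planned rate is always the lower one. Where abandonment had unrelated causes (b = 0), the rate over attempts is slightly lower: for x = 3 and a = 5 it is 3/186 = 1.61% against 3/181 = 1.66%.

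**3. Illustration (x, a and b are all assumed, with b = a).** With x = 3, the planned rate is 3/181 = 1.7% (exact 95% interval 0.3 to 4.8).

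- a = 2: 5/183 = 2.7% (0.9 to 6.3)
- a = 4: 7/185 = 3.8% (1.5 to 7.6)
- a = 6: 9/187 = 4.8% (2.2 to 8.9)

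A wider grid, again with b = a:

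| x | planned, x/181 | a = 1 | a = 2 | a = 5 | a = 10 |
|---|---|---|---|---|---|
| 0 | 0.00% | 0.55% | 1.09% | 2.69% | 5.24% |
| 2 | 1.10% | 1.65% | 2.19% | 3.76% | 6.28% |
| 5 | 2.76% | 3.30% | 3.83% | 5.38% | 7.85% |
| 10 | 5.52% | 6.04% | 6.56% | 8.06% | 10.47% |

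With a = 0 the two rates are identical.

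**4. Partial implantation.** Sections 3.3 and 10.3 name three required components. Section 9.4.4.2 speaks only of receiving the system and does not repeat the list. Section 10.3 refers to the device not being implanted, and 11.6 to component(s) not being implanted. A subject with one or two of the three components could be a recipient with a deviation or a non-recipient. The text does not say which.

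**The case against.** **The events are not hidden.** They are collected from consent, all adverse events are to be listed, and censored cases are to be reported separately. This stands, and it limits the point to the rates and intervals. A reader might infer that the worst intraoperative outcomes disappear from the study. The documents do not support that. A listing still does not put a case back into a percentage.

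**The causal chain is not documented.** Nothing says that a fracture leads to abandonment. Section 6.1 provides stems for added stability and augments for poor bone stock, and a fracture case that still receives the system stays in numerator and denominator. This stands as well. The bias is possible and its frequency is unknown.

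**The illustration builds in its answer.** With 3 events in implanted cases and 2, 4 or 6 abandoned ones, it supposes that 40%, 57% or 67% of all such events end in abandonment. The results for two and four cases, 2.7% and 3.8%, also lie inside the planned interval of 0.3 to 4.8. Both remarks are fair. The figures show direction and sensitivity and are not an estimate.

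**Partial recipients.** A reader might infer that anyone lacking one required component is outside the Safety Population, is terminated on the day of surgery, and goes without study follow-up while carrying study components. The documents do not establish this. The requirement for the full set is an inference from 3.3 and 10.3, section 10.3 says only that subjects may be withdrawn, and one event can be both a deviation and a withdrawal reason. What remains is an unclear classification.

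**Convention and comparability.** A recipient-based safety set is common for a post-market implant study. The literature comparison is descriptive, with no threshold or test, and the documents do not show which denominator the published series use. This argues for showing implanted cases as a subset. It does not argue for leaving attempted cases out of every denominator.

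**Conclusion.** The point holds as a gap in the denominator. No population in the plan contains an attempted but abandoned implantation, so an event that caused abandonment cannot enter the adverse event rates or their intervals. For intraoperative and early events those rates can be too low, and they are too low whenever the share of abandoned cases with the event exceeds the rate among implanted cases.

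The size cannot be derived from the documents. It is zero with no abandoned case. Under the stated assumptions, two such cases move 1.7% to 2.7%. The conclusion rests on reading 9.2.2 as using the Safety Population, the only safety population defined. This is an inexpensive improvement to the plan and does not show that the safety results would mislead. The status of partial recipients is a separate ambiguity to be settled in the text.

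**What to change.** 1. In 9.4.4.2, define the Safety Population as every subject in whom implantation of any Triathlon TS component was attempted, and say what counts as an attempt.
2. In 9.2.2, name that denominator for intraoperative and early adverse event rates, state where the early period ends, and show the same rates for implanted cases as a subset.
3. State in 9.4.4.2 and 9.4.4.4 that non-implantation is not in itself a ground for censoring from the Safety Population. Otherwise the deviation entry in 11.6 could remove these subjects again.
4. Reconcile 9.4.4.2, 10.3 and 11.6 on how a subject who receives only some of the required components is classified.
5. Leave the efficacy population and the count of 181 unchanged.

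The cost is protocol and SAP wording and a few extra subjects in the safety tables. The wider denominator may differ from that of some published series, and the implanted subset covers that case.

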## Primary:

	A one-sided 95% confidence interval of the total KSS change from preoperative to 2 years postoperative (2 years - preoperative) will be computed at 2 years postoperative. For the non-inferiority comparison, the lower bound of this confidence interval will be compared with 63 points (10% worse than the expected improvement). For the superiority comparison, the lower bound of this confidence interval will be compared with 70 points (the expected improvement).
Statistical Methodology	Secondary:
	An independent group t-test or a nonparametric test will be used to
	compare the secondary numerical parameters (e.g. KSS, HSS, KOOS)
	between the JL restoration subgroups at 1, 2 and 5 years
	postoperative; and a Chi-square test or Fisher's exact test will be used
	to compare the secondary categorical parameters (e.g. postoperative
	stability, anterior knee pain and functional performance) between the
	subgroups. In addition, a paired t-test or Wilcoxon rank sum test will be
	used to compare the change in outcomes other than the KSS from
	preoperative to 1, 2 and 5 years postoperative within the Triathlon TS
	Total Knee System group. The radiographic stability rates, adverse
	event (AE) rates and revision rates with 95% confidence intervals will
	be presented in tables.

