### CONFIDENTIAL

### 2.1.2 Secondary

The secondary objectives of this study will be to evaluate the effect of JL restoration on revision TKR with specific reference to effect on postoperative stability, anterior knee pain and functional performance at 2 and 5 years postoperatively. It is expected that the Triathlon® TS group with JL elevation > 5 mm is non-inferior to the Triathlon TS group with JL elevation  $\leq$  5 mm.

All outcomes other than the change in KSS, already analyzed as the primary objective, will be analyzed from preoperative to 1, 2 and 5 years postoperatively.

Additionally, the long-term performance of the Triathlon TS Total Knee System for revision TKR will be evaluated with regard to radiographic stability, revision rate and complications when reviewed against published data.

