## 2.2 Safety

All operative site events as well as all serious adverse events (SAEs), excluding elective procedures, will be collected and reviewed against published data. It is expected that the AE rates reported for the Triathlon TS Total Knee System will be comparable to those reported in

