## 9.2 Safety Parameters

### 9.2.1 Safety Parameters

Safety parameters will include all AEs reported, radiographic stability at 1, 2 and 5-year visits and revision rates.

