## 9.2.2 Safety Analysis

All AEs will be listed, tabulated and summarized by event, number and percent of cases/subjects. AE rates and 95% confidence intervals will be presented. In addition, a Fisher's exact test will be used to compare the AE rates between the subgroups or cohorts, if appropriate.

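### The Safety Population drops implanted cases with outcome-relevant protocol deviations, so the pooled safety rates compared with published data need not cover every implanted case

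*Combined protocol and SAP*

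**What the plan says.** Section 9.4.4.2 (Safety) begins with all subjects who receive the Triathlon TS system and then adds: "This does not include cases censored from analysis for a reason that may have a significant impact on outcome". Section 9.4.4.1 uses the same sentence for the per protocol efficacy set.

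Section 9.4.4.4 (Censored Cases) gives the trigger, a protocol deviation with the potential to influence the subject's outcome, and the consequence: "the data for the affected subject will be censored from the Efficacy and Safety Subject Populations". It adds: "All cases that fall into this category will be reported separately".

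Section 9.4.4.3 (Survival Analysis) uses a modified intent-to-treat set of enrolled subjects who received the device, without this exclusion.

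The outputs concerned are in section 9.2. Section 9.2.1 states: "Safety parameters will include all AEs reported, radiographic stability at 1, 2 and 5-year visits and revision rates". Section 9.2.2 states: "AE rates and 95% confidence intervals will be presented", and gives numbers and percentages for radiographic stability, revision and complications. The Synopsis (Statistical Methodology) plans intervals for revision rates as well.

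Three places set these results against the literature. Section 2.2 says: "All operative site events as well as all serious adverse events (SAEs), excluding elective procedures, will be collected and reviewed against published data". Section 2.1.2 says that long-term performance "will be evaluated with regard to radiographic stability, revision rate and complications when reviewed against published data". Section 12.3 repeats the comparison for complication rates.

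**The concern.** A safety set normally contains everyone exposed to the product. Here it is in effect a second per protocol set. The rule looks at what a deviation might do to outcome, not at the outcome observed, but it still removes people who carry the implant.

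The rule is also open-ended. No section lists the qualifying deviations, names who judges them, or says when. The deviation list in section 11.6 is expressly not exhaustive. It includes enrolling patients who fail the eligibility criteria, which under section 4.2 could mean a BMI above 40 or an infection at implantation. Section 12.4 foresees deviations made to protect a subject's health. Such cases could plausibly be judged relevant to outcome, so exclusion need not be unrelated to risk.

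There is no concurrent control arm. The pooled rate is therefore all that the study brings to the comparison with published data. If implanted cases are left out, the rate is too low when those cases had more events and too high when they had fewer.

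**Working it through.** **1. Which population feeds which output**

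| Output | Section | Population named there? | Implanted cases with a qualifying deviation |
|---|---|---|---|
| Primary and secondary efficacy | 9.4.4.1 | Yes, per protocol | Removed |
| AE rates with 95% CI | 9.2.2, Synopsis | No | Removed if the Safety Population is used |
| Radiographic stability, tabulated revision rates, complications | 9.2.1, 9.2.2 | No | Removed if the Safety Population is used |
| Survival analysis | 9.4.4.3 | Yes, modified intent-to-treat | Kept |

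Section 9.2 names no population. A set defined for analysis under the heading Safety has no other evident use, so applying it to section 9.2 is the natural reading. Revisions then have two denominators: a reduced one in the tables and the full one in the survival analysis.

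**2. The plan's own figures**

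The plan gives no safety event rate and no expected number of censored cases. The figure available is the sample size in section 9.4.2 (SD 35, margin 7, one-sided alpha 0.05, power 80%, 15% loss):

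- n = (35 × (1.645 + 0.842) / 7)² = 154.6, against 154 stated.
- 154 / 0.85 = 181.2, against 181 stated.

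These reproduce to within rounding. The full safety denominator is therefore 181 planned implanted cases, or 181 − k when k are censored.

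**3. Effect on a pooled rate**

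Assumptions, none from the documents: retained-case event rate 5%; censored fraction f of 2%, 5% or 10%; relative risk RR in censored cases from 0 to 4.

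All-implanted rate = (1 − f) × 5% + f × 5% × RR.

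CI half-width = 1.96 × √(0.05 × 0.95 / n), with n the retained cases.

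| f | Retained n | RR 0 | RR 1 | RR 2 | RR 3 | RR 4 | Half-width (points) |
|---|---|---|---|---|---|---|---|
| 2% | 177 | 4.90% | 5.00% | 5.10% | 5.20% | 5.30% | 3.21 |
| 5% | 172 | 4.75% | 5.00% | 5.25% | 5.50% | 5.75% | 3.26 |
| 10% | 163 | 4.50% | 5.00% | 5.50% | 6.00% | 6.50% | 3.35 |

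The reported figure is 5.0% throughout. Relative to the all-implanted rate:

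- f = 2%: from 2.0% too high (5.0/4.90) to 5.7% too low (5.0/5.30).
- f = 5%: from 5.3% too high (5.0/4.75) to 13.0% too low (5.0/5.75).
- f = 10%: from 11.1% too high (5.0/4.50) to 23.1% too low (5.0/6.50).

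The largest absolute shift is 6.50 − 5.00 = 1.5 points, less than half of its half-width.

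**4. Secondary: the same rule in the primary KSS test**

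With f = 5%, evaluable n = 154 × 0.95 ≈ 146 and SE = 35/√146 = 2.897. Suppose censored cases gain d points less than retained cases and the all-implanted mean change sits at the 63-point bound. The one-sided rejection probability is 1 − Φ(1.645 − 0.05 × d / 2.897):

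- d = −10 (censored cases gain more): 3.5%.
- d = 0: 5.0%.
- d = +10 (censored cases gain less): 7.0%.

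This is error with respect to an all-implanted mean, which the plan does not make its primary target. It does not drive the conclusion here.

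**The case against.** The strongest reply is that no sentence ties section 9.2 to the Safety Population, whereas 9.4.4.1 does make that tie for efficacy. Section 9.2.2 also speaks of listing and tabulating all AEs, which could mean every implanted case. This shows that the link is an inference. It does not rescue the text: on that reading 9.2.2 contradicts 9.4.4.2 and 9.4.4.4, and the sections still have to be reconciled.

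Second, censored cases are reported separately, so nothing is hidden, and collection of AEs is unaffected. That is a real mitigation, because a careful reader would know that the pooled rate omits them. But 9.4.4.4 does not require the separate report to give case counts and events by type. Without those the all-implanted rates cannot be rebuilt, and no pooled interval is planned.

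Third, the survival analysis already covers revision in all implanted subjects. That is true, but it does not cover AE rates or radiographic stability.

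Fourth, several deviation types in section 11.6, such as consent-form errors, are unlikely to qualify, and if none does, coverage is complete. This stands: the effect is conditional, and the fractions in the illustration have no basis in the documents.

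Fifth, the effect is small, its direction unknown, and no formal safety test depends on it. This also stands, and it limits the severity. A confidence interval, however, describes sampling error and does not correct for cases excluded by rule.

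**Conclusion.** The concern holds. Sections 9.4.4.2 and 9.4.4.4 expressly remove some implanted cases from the safety set, and on the natural reading the pooled rates compared with the literature omit them. That sits poorly with the safety objective in section 2.2, which takes in all operative-site events and all non-elective SAEs.

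Under the assumed inputs the distortion is modest, in either direction, and absent at equal risk. The documents support incomplete coverage; they do not establish the size or sign of a bias. The point should be fixed because a stated rule can bias a headline descriptive result and is nearly free to remove. It is not critical to the trial's primary conclusion.

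**What to change.** **Main change, in three places**

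- Section 9.4.4.2: delete the second sentence, so that the Safety Population is every case that received the Triathlon TS system.
- Section 9.4.4.4: remove safety from the censoring rule. Keep the separate report of deviation cases as a supplementary listing.
- Section 9.2.2: state that AE, radiographic and revision rates, with their intervals, use this population.

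**Secondary, for efficacy**

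- Leave the per protocol KSS analysis and its success rule as they are, and add one sensitivity analysis in all implanted cases with 2-year data.
- List the deviations that exclude a case from the per protocol set, and decide them without sight of KSS results where that is still possible. Section 1.4 reports that early study data were presented in 2012; the abstract summarised there concerns femoral offset use and gives no KSS results.

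**Cost**

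The cost is wording, a short list and one extra analysis. No new data are needed. The safety rates may look slightly less favourable if the censored cases had more events.
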